3 ANALYSIS SETS

The following analysis sets for analyses are defined:

Table 4 - Analysis Sets

Analysis Set	Description
Screened	All participants who signed the ICF.
Enrolled	All eligible participants who are dispensed Soliqua 100/33 and sign the ICF.
Efficacy analysis set	All enrolled participants who receive ≥ 1 dose of Soliqua 100/33 and have compliant ^a CGM data at baseline.
Safety set	All enrolled participants who receive ≥ 1 dose of Soliqua 100/33.

- a. CGM compliance is defined as 1) at least 8 out of 14 days (not necessarily consecutive) have 100% of evaluable CGM data per 24-hour period (at least 8 days with 96 records minimum per day) OR 2) at least 9 out of 14 days (not necessarily consecutive) have $\geq 89\%$ of evaluable CGM data per 24-hour period (at least 9 days with 85 records minimum per day) OR 3) at least 10 out of 14 days (not necessarily consecutive) have at least $\geq 80\%$ of evaluable CGM data per 24 hour period (at least 10 days with 77 records minimum per day)

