The following intercurrent events for the primary estimand will be handled by the treatment policy strategy: initiation of rescue medication other than the study IMP, discontinuation of IMP, withdrawal from the study, and recording of <80% of evaluable CGM data per 24-hour period over 10 days of a 14-day period, during the run-in period as well as the end of the treatment period (ie, from Weeks 14 to 16; Section 13.9). This estimand aims to reflect the estimated treatment effect under the intention-to-treat (ITT).

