8.4 Analysis Sets

The following analysis sets will be used in the statistical analyses:

- Enrolled set: All eligible participants who are dispensed Soliqua 100/33 and sign the ICF.
- Efficacy analysis set: All enrolled participants who receive ≥1 dose of Soliqua 100/33 and have evaluable CGM data at baseline.
- Safety set: All enrolled participants who receive ≥ 1 dose of Soliqua 100/33.

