4.2 PARTICIPANT DISPOSITIONS

The number (%) of participants included in each of the analysis sets listed in [Table 4](#) will be summarized. The participants excluded from the efficacy set will be displayed in a listing. A separate listing will be created for those who are excluded from the efficacy set due to technical issues from the CGM device.

Screen failures are defined as participants who consent to participate in the study but are not subsequently enrolled (i.e., do not have IMP dispensed subsequently). The number (%) of screen failures and reasons for screen failures will be provided in the screened set disposition descriptions.

The number (%) of participants in the following categories will be provided:

- Screened participants
- Enrolled participants
- Enrolled but not exposed participants
- Enrolled and exposed participants
- Participants who completed the 16-week study treatment period as per protocol
- Participants who completed the entire study period as per protocol (22 weeks).

- Participants who did not complete the study period as per protocol and did not record a main reason for study discontinuation
- The number (%) of exposed and non-enrolled participants will also be summarized.
- Final study status

Additionally, trial impact (disruption) due to COVID-19 will be summarized for the safety set using number and percentage. Participants for whom at least one of the following events occurred during the study will be presented:

- Permanent discontinuation of treatment due to COVID-19, defined as participants whose “Main Reason for Premature End of Treatment” on End of Treatment eCRF page is “Adverse Event”, and a corresponding adverse event of “Covid-19” with “Drug withdrawn” as the response to “Action Taken with Study Treatment” on the Adverse Events eCRF page.
- Permanent discontinuation of treatment due to AE related to COVID-19 infection, defined as participants whose “Main Reason for Premature End of Treatment” on End of Treatment eCRF page is “Adverse Event”, and a corresponding adverse event of “AE Term due to Covid-19” with “Drug withdrawn” as the response to “Action Taken with Study Treatment” on the Adverse Events eCRF page.
- Premature end of treatment due to COVID-19 pandemic, defined as participants whose “Main Reason for Premature End of Treatment” on the End of Treatment eCRF page is “Other”, and in “If Other, specify” beginning the Specify comment following text “Covid-19:”.

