An overdose (accidental or intentional) with the IMP is an event suspected by the Investigator or spontaneously notified by the participant and defined as at least twice the intended dose within the intended therapeutic interval (planned treatment period), adjusted according to the tested drug. Cases of symptomatic overdoses will constitute AESIs and will be listed as such.

The AE tables will be sorted as indicated in [Table 5](#).

Table 5 - Sorting of AE tables

AE presentation	Sorting rules
SOC, HLG, HLT and PT	By the internationally agreed SOC order and by alphabetic order of HLGs, HLTs and PTs.
SOC and PT	By the internationally agreed SOC order and decreasing frequency of PTs ^{a, b}

^a Sorting will be based on the mg dose intervention group/overall incidence.

^b Within each table the sorting will be by the internationally agreed SOC order and decreasing frequency of PTs; in case of tie for PT, the sorting will be alphabetical.

Analysis of all AEs

The overview of TEAE with the details below will be generated (number and percentage of participants) in a table:

- Any TEAE
- Any treatment emergent SAE
- Any treatment emergent AESI
 - Pregnancy.
 - Symptomatic overdose.
 - Increase in ALT (>3 × ULN).
- TEAE leading to death (death as an outcome of the AE as reported in the AE page)
- Any TEAE leading to temporary IMP discontinuation.
- Any TEAE leading to permanent IMP discontinuation

- Any treatment-related TEAE
- Any TEAE leading to study discontinuation

The overview summary for TEAEs will be provided on the safety set and will be repeated on the subgroup of safety participants according to trial impact (disruption) due to the COVID-19 pandemic.

Individual listings (AEs, SAEs, AEs leading to death, TEAEs leading to permanent IMP discontinuation, AESI, AEs for Treated and not enrolled participants) will be provided to support the summary tables based on the safety set.

A listing of all participants who died during the study will be provided.

The AE summaries of [Table 6](#) will be generated with number (%) of participants experiencing at least one event.

Table 6 - Analyses of adverse events

Type of AE	MedDRA levels
All TEAE	Primary SOC, HGLT, HLT and PT
Common TEAE (≥5%)	Primary SOC and PT
TEAE related to IMP	Primary SOC, and PT
TEAE by maximal severity	Primary SOC and PT
Treatment emergent SAE	Primary SOC and PT
TEAE leading to study discontinuation	Primary SOC and PT
TEAE leading to permanent discontinuation of IMP	Primary SOC and PT

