data will be downloaded on the fifteenth day after CGM placement (ie, Visit 7; after collection of only plasma glucose data from the MMTT). Downloaded CGM data will be verified by the investigator at the site to determine participants' study completion.

r Participants who do not meet CGM compliance criteria at baseline will be considered screen failures.

s Participants will undergo the MMTT to assess maximum PPG exposure in the 4-hour period after the breakfast meal with biomarkers of β -cell function (plasma glucose, insulin, and C-peptide) measured at Visit 3.1 (ie, site visit during the baseline period), whereas only plasma glucose will be assessed at Visit 7 (ie, end of the treatment period).

t Participants should discontinue GLP-1RA, DPP-4i, or down-titrate SU medications after all baseline assessments have been completed. SU doses should be down-titrated by 50% when starting Soliqua 100/33, whereas the last dose of daily DPP-4i and daily GLP-1RA (oral or injectable) should be administered on the morning of Day -1, the day before the first dose of Soliqua 100/33.

Participants on weekly GLP-1RA should administer their last dose 7 (\pm 2) days before the first dose of Soliqua 100/33.

u Soliqua pen instructions will be given to all participants at Visit 3.1. A phone contact should be made to **participants on weekly GLP-1RA** on the day **before Soliqua 100/33 initiation**, to remind them of the next morning's injection and to provide instructions for SoloStar pen use.

v For the scheduled site visits, participants are required to arrive fasting without administering the Soliqua 100/33 injection. Fasting is defined as no food intake in the 8 hours before blood sampling, except water.

w Baseline DM-SAT should be completed before discontinuation or down-titration of baseline therapies. The questionnaire should be completed at the start of the visit before any other study tests or procedures are performed or Soliqua 100/33 is administered.

x The following hypoglycemia categories of interest will be presented: overall hypoglycemia and confirmed hypoglycemia (ADA Levels 1, 2, and 3; Section 6.3.2).

y Urinalysis: pH, glucose, ketones, leukocytes, blood/Hb, protein.

z Only for women of childbearing potential; urine pregnancy test.

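### The safety set is drawn from an enrolled set limited to eligible participants, with no time set for that judgement, so on a literal reading a dosed but ineligible participant is missing from the main safety tables

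*SAP*

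**What the plan says.** SAP Table 4 defines the enrolled set as "All eligible participants who are dispensed Soliqua 100/33 and sign the ICF". Protocol 8.4 has the same definition: "Enrolled set: All eligible participants who are dispensed Soliqua 100/33 and sign the ICF". The SAP safety set is "All enrolled participants who receive ≥ 1 dose of Soliqua 100/33". The efficacy analysis set starts from the same words and adds "and have compliant ^a CGM data at baseline". Both sets therefore inherit the eligibility condition.

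The SAP also foresees people who took the drug but are not enrolled. Section 4.2 states: "The number (%) of exposed and non-enrolled participants will also be summarized". Section 4.7.2 lists, among the individual listings meant to support summary tables on the safety set, "AEs for Treated and not enrolled participants".

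Footnote r to the schedule of events in SAP 5.4.5 states: "Participants who do not meet CGM compliance criteria at baseline will be considered screen failures". SAP 4.2, however, describes a screen failure as someone who consented and did not go on to have study drug dispensed.

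**The concern.** A safety set should answer one question: who took the drug? Here it also depends on eligibility, a word that neither document fixes in time. If a programmer takes it to mean confirmed eligible, a participant dosed in breach of a criterion leaves the denominators and numerators of the treatment-emergent adverse event, hypoglycemia and exposure tables, together with their person-time.

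Such a loss need not be neutral. The exclusion criteria in Protocol 4.2 cover recent severe hypoglycemia, clinically significant pancreatitis and severe renal impairment. People entered in breach of these could plausibly have more events than the rest, though the documents contain no data on this. In a single-arm study the safety result is purely descriptive, so the choice of denominator is much of the analysis.

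**Working it through.** The point turns on definitions, so the main check sets the sections side by side. A short calculation on size follows.

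**1. What depends on the word.**
- SAP 4.7 puts all safety analyses on the safety set unless otherwise specified. SAP 4.7.1 does so for exposure and adherence, SAP 4.7.2 for treatment-emergent and post-treatment adverse events, and Protocol 8.7.8.2 for hypoglycemia.
- CGM efficacy uses the efficacy set. Maximum postprandial glucose, HbA1c and treatment satisfaction use the enrolled set (SAP 4.4.1.1, 4.5.1). All of these carry the eligibility condition.
- Pre-treatment adverse events use the screened set (SAP 4.7.2) and do not.

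**2. Two readings of eligible.**
- *Judged eligible at dispensing.* SAP 4.2 equates not being enrolled with not having drug dispensed. SAP 5.4.5 places enrollment at Visit 3.2, the first dose. Protocol 11.2.2 treats breaches of entry criteria as significant deviations, and SAP 5.3.1 summarizes significant deviations in the enrolled set, which could not show those breaches if they removed the person from the set.
- *Confirmed eligible.* If dispensing or first dose alone made someone enrolled, the planned count of exposed, non-enrolled participants and the listing of their adverse events would have almost nobody to describe. They have content mainly if eligibility can remove a dosed person.

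The SAP contains support for both readings and does not choose.

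**3. Can it happen?** HbA1c is drawn at Visit 3.1 (Day -1), and Protocol 6.2.5 gives eligibility as a purpose of that sample. Protocol 6.5 returns central laboratory results in 48-72 hours. Drug is dispensed at Visit 3.1 and the first dose is on Day 0, normally the next day, or about 24 hours later. The result can therefore arrive 24 to 48 hours after the first dose (48 - 24 and 72 - 24). Some weekly GLP-1 RA users start later and would escape this. Inclusion criterion 3 requires HbA1c in range during the run-in, which includes both Visit 2 and Visit 3.1, and does not say which value governs.

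**4. Footnote r.** Protocol 6.2.1 has sites admit on days worn × % time active, with at least 8 equivalent days. Thirteen days at 62% gives 13 × 0.62 = 8.06, and Table 6-1 lists this combination as sufficient. If the gaps are spread evenly, every day is at 62%, so no day reaches the 80%, 89% or 100% needed by the three options of the SAP compliance rule. That person is properly dosed under the protocol, yet footnote r makes them a screen failure. This conflicts with SAP 4.2. It also sits badly with Table 4, where baseline CGM compliance is a condition of the efficacy set only.

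**5. Size.**
- Planned sample size: n = (25 × (1.960 + 1.645) / 10)² = 81.2, rounded up to 82, as stated. With 15% loss, 82 / 0.85 gives 97, against 100 planned. None of this depends on the set wording.
- Number affected (k): not given, so assumed. Leaving out k = 1, 2, 5 or 10 of 100 dosed participants gives safety denominators of 99, 98, 95 or 90.
- One event: if the one person left out had the only ADA Level 3 event, 1/100 (exact 95% upper limit 5.4%) becomes 0/99 (upper limit 3.7%).
- Power, if all k came out of the 82 evaluable: the exact t-test gives 94.7% at 82, and 94.5%, 94.2%, 93.4% or 91.7% after losing 1, 2, 5 or 10.

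**The case against.** The strongest reply is that eligible stands beside dispensed, that eligibility is checked at Visit 3.1 when the drug is handed out, and that the sections listed under the first reading in step 2 point to keeping a late-found ineligible participant enrolled. That stands as an argument about probable intent. It does not remove the ambiguity, because the SAP also plans outputs for exposed, non-enrolled people.

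A reader might infer that such participants vanish from every safety summary. The documents do not support that: a disposition count and an adverse event listing are planned for them, and pre-treatment events use the screened set. What remains is that they are missing from the treatment-emergent, hypoglycemia and exposure tables, and that their listing is tied to tables on a set that excludes them.

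A reader might also infer a breach of the intention-to-treat aim in Protocol 8.1. That sentence concerns intercurrent events for the primary time-in-range estimand. Ineligibility is not among the events listed there, and the sentence does not bear on the safety set.

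Finally, footnote r can be read as a pre-dosing rule, since it annotates the Visit 3.1 compliance check, and Table 4 already confines baseline CGM compliance to the efficacy set. That is largely right, so footnote r is a secondary inconsistency and not the main route to exclusion.

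**Conclusion.** The safety set should not depend on eligibility or enrollment status, and as written it does. On the literal reading, dosed but ineligible participants are outside the treatment-emergent adverse event, hypoglycemia and exposure tables and the efficacy analyses. The SAP's own provision for treated, non-enrolled people makes that reading credible, and the timing of the Visit 3.1 HbA1c result makes the case possible in practice.

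It would go too far to say that these participants will be dropped, or that the safety profile will look better than it was. The first depends on an undefined word, and the second on how many such people there are and what happened to them; the documents give neither. The denominators and the 1/100 against 0/99 example in the working are illustrations under assumed counts. If nobody is dosed while ineligible, nothing changes. This is a SHOULD-FIX.

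**What to change.** Before database lock:

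- Define the safety set in SAP Table 4 as all participants who receive at least one dose of Soliqua 100/33, regardless of eligibility or enrollment status.
- Remove eligible from the enrolled set, or state that it means judged eligible at the time of dispensing.
- Base the listing of adverse events in treated, non-enrolled participants (SAP 4.7.2) on all dosed participants.
- Reconcile footnote r with SAP 4.2 and Table 4, so that a dosed participant with non-compliant baseline CGM is left out of the efficacy set only and is not counted as a screen failure.
- Carry the set definitions into Protocol 8.4 at the next amendment, and record the change in the SAP's table of deviations from the protocol.

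The cost is wording. No new data are needed, and the sample size, power and alpha stay as stated. The small downside is that a few participants with eligibility deviations enter the safety tables. They remain identifiable through the deviation listing in SAP 5.3.1, provided the enrolled set is changed as above.

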4 STATISTICAL ANALYSES

The database lock will be performed when all participants have completed their follow-up phase. Final analyses in the clinical study report will be based on all data collected up to this database lock.

4.1 GENERAL CONSIDERATIONS

In general, continuous data will be summarized using the number of observations available, mean, standard deviation (SD), quartile ranges, median, minimum, and maximum.

All mean, Q1, Q3 and median values will be formatted to one more decimal place than the measured value. SD values will be formatted to two more decimal places than the measured value. Minimum and maximum will be formatted to the same number of decimal places as the measured value.

Unless otherwise specified below, all confidence intervals (CI) will be two-sided at the 95% confidence level and displayed to the same level of precision as the statistic they relate to. If an estimate or a CI is not estimable, it will be presented as 'NE'. If neither an estimate, nor its CI are estimable, it will be presented as simply 'NE', not displaying 'NE' twice.

The p-values will be two-sided and will be rounded to three decimal places. If a p-value is less than 0.001 it will be reported as '<0.001'. If a p-value is greater than 0.999 it will be reported as '>0.999'.

Categorical data will be summarized using the count and percentage of participants. When count data are presented, the percentage will be suppressed when the count is zero in order to draw attention to the non-zero counts. A row denoted 'Missing' will be included in count tabulations for demographics, baseline characteristics and compliance to account for missing values. No percentages will be displayed on the 'Missing' rows and the percentages on the other rows will be based on the number of non-missing observations. Unless otherwise specified, the denominator for all other percentages will be the number of participants in that treatment within the specific analysis set of interest. All percentages will be rounded to one decimal place. The number and percentage of responses will be presented in the form xx (xx.x), where the percentage is in the parentheses. When the numerator is equal to the denominator, the percentage should be presented as (100) instead of (100.0), unless otherwise specified.

The baseline value is defined as the last available value before the first injection of Soliqua 100/33. Participants enrolled but not treated will have a last available measurement following enrollment.

If multiple valid values of a variable (efficacy or safety) exist within a same day (and the recorded times of measurement do not identify which of them is the last assessment), the value measured during the scheduled visit will be used as Baseline in the analysis. If none of those values were assessed during a scheduled visit, then all these measurements will be used for the analysis and the average will be calculated to derive the baseline value.

In general, descriptive statistics of quantitative efficacy and safety parameters (result and change from baseline) by scheduled visits will be provided on observed cases (OC; ie, inclusion of only participants having non-missing assessments at a specific visit).

Baseline safety and baseline efficacy results are presented in the safety and efficacy analyses, respectively.

All safety analyses will be performed on the safety analysis set.

Statistical analysis will be performed using SAS Enterprise software Version 9.4 or higher.

Observation period

The observation period will be divided into 3 segments:

- The **pre-treatment period** is defined as the period up to first IMP administration. There are two periods within pre-treatment period. A 2-week screening period and a 2-week run-in period.
- The **on-treatment period** (ie, treatment-emergent (TE) period) is defined as the period from the first IMP administration to the last IMP administration during Visit 7 (Week 16).
- The **post-treatment period** is defined as the period from the end of the on-treatment period to the end of the 2-week safety period. (Week 18)

4.2 PARTICIPANT DISPOSITIONS

The number (%) of participants included in each of the analysis sets listed in [Table 4](#) will be summarized. The participants excluded from the efficacy set will be displayed in a listing. A separate listing will be created for those who are excluded from the efficacy set due to technical issues from the CGM device.

Screen failures are defined as participants who consent to participate in the study but are not subsequently enrolled (i.e., do not have IMP dispensed subsequently). The number (%) of screen failures and reasons for screen failures will be provided in the screened set disposition descriptions.

The number (%) of participants in the following categories will be provided:

- Screened participants
- Enrolled participants
- Enrolled but not exposed participants
- Enrolled and exposed participants
- Participants who completed the 16-week study treatment period as per protocol
- Participants who completed the entire study period as per protocol (22 weeks).

- Participants who did not complete the study period as per protocol and did not record a main reason for study discontinuation
- The number (%) of exposed and non-enrolled participants will also be summarized.
- Final study status

Additionally, trial impact (disruption) due to COVID-19 will be summarized for the safety set using number and percentage. Participants for whom at least one of the following events occurred during the study will be presented:

- Permanent discontinuation of treatment due to COVID-19, defined as participants whose “Main Reason for Premature End of Treatment” on End of Treatment eCRF page is “Adverse Event”, and a corresponding adverse event of “Covid-19” with “Drug withdrawn” as the response to “Action Taken with Study Treatment” on the Adverse Events eCRF page.
- Permanent discontinuation of treatment due to AE related to COVID-19 infection, defined as participants whose “Main Reason for Premature End of Treatment” on End of Treatment eCRF page is “Adverse Event”, and a corresponding adverse event of “AE Term due to Covid-19” with “Drug withdrawn” as the response to “Action Taken with Study Treatment” on the Adverse Events eCRF page.
- Premature end of treatment due to COVID-19 pandemic, defined as participants whose “Main Reason for Premature End of Treatment” on the End of Treatment eCRF page is “Other”, and in “If Other, specify” beginning the Specify comment following text “Covid-19:”.
- Premature end of study due to COVID-19 pandemic, defined as participants whose “Reason for End of Study/follow-up period” on the Completion of End of Study eCRF page is “Other”, and in “If Other, specify details” beginning the Specify comment following text “Covid-19:”

